4 STUDY DESIGN

This study is a phase 1, randomized, double-blind clinical trial designed to evaluate the safety, tolerability, and immunogenicity of single-vial lyophilized ID93 + GLA-SE compared to the two-vial presentation consisting of lyophilized ID93 and liquid GLA-SE administered as two intramuscular injections in healthy adult subjects.

This study will enroll 48 healthy subjects aged 18 to 55. Subjects will be counseled on the study and will then give an informed consent. Screening will be performed that will include evaluation of medical history, medication history, a physical examination, and safety laboratory evaluations. Subjects who meet all eligibility criteria will be randomized 1:1 into the two treatment groups. Study injections will be performed and subjects will be observed in clinic for 60 minutes. All subjects will complete a written subject memory aid that solicits local and systemic reactogenicity adverse events for 7 days following each study injection. Subjects will undergo a second study injection on Day 56. General safety will be evaluated on Days 0, 7, 56, 63, and 84 for each subject. All data will be recorded in the source document during the study period.

Non-serious adverse events will be collected through Day 84 (28 days following the last study injection). The occurrence of serious adverse events (SAEs) and the new onset of any potential immune-mediated medical conditions (PIMMCs) will be collected throughout the study period (approximately 421 days).

The details of all study visits are outlined in [Section 7](#). Each subject's duration of participation will be about 14 months. A detailed outline of the study visits and procedures is provided in the Study Visit Schedule ([Appendix 1](#)). Immunogenicity will be assessed on Day 0 (pre-dose) and on Days 7, 14, 56, 63, 70, 84, and 224. Blood will be assessed for safety laboratories on the day of screening, and on Days 7 and 63. Urinalysis will be performed at screening.

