11.5.3 Immunology Analyses

Immunogenicity will be assessed from blood samples obtained on Days 0, 7, 14, 56, 63, 70, 84, and 224. Secondary immunogenicity evaluations will include quantification of T cell cytokine responses from stimulated PBMCs and serum IgG antibody responses to ID93. Exploratory analyses will include measurement of functionality of immune responses through the whole blood mycobacterial growth inhibition assay (MGIA), measurement of humoral responses in mucosal secretions (nasal swabs and tears), quantitation of IgA and IgG secreting B cells and memory B cells, and measurement of the frequencies of peripheral T follicular helper cells, memory B cells, and T cell homing markers.

Immune responses for each treatment group will be evaluated by calculating the response rate and magnitude of response to ID93 at all timepoints for each immunologic endpoint. Comparisons of response rates for IgG and cytokine responses across treatment groups will be made using $n \times m$ Fisher's exact tests. Pairwise comparisons will be done using 2×2 Fisher's exact tests with multiplicity adjustment to control the family-wise error rate (FWER).

The magnitude of IgG and cytokine responses will be compared across treatment groups using ANOVA when the distribution is Gaussian and Kruskal-Wallis when the distribution is non-Gaussian. When ANOVA is used and a difference is observed across the treatment groups, pairwise comparisons will be made using t-tests with adjustment to control the FWER. If Kruskal-Wallis is used, Wilcoxon rank-sum tests will be used.

Percentages of CD4 and CD8 T cells producing selected cytokines will be summarized by time point and compared across and between treatment groups.

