7.2 Plan for Statistical Summaries and Analyses

7.2.1 General Considerations

Statistical summaries and analyses of baseline and safety data will be provided for the safety population, defined as all subjects who receive at least one study injection. Summaries and analyses of immune response data will be provided for the per-protocol population. The objectives of the immune response statistical summaries and analyses are to assess the immunogenicity following intramuscular administration of study vaccine among the treatment groups. The goals are:

1. To describe the humoral and cellular response to both vaccine presentations in terms of magnitude and positive response rate
2. To determine if there is a significant difference in the immune response elicited by the two-vial and the single-vial lyophilized vaccine presentation

All individual subject data listings will be provided in appendices to the clinical study report. Data will be summarized and tabulated by treatment group and descriptive statistics will be provided where

appropriate. The immunology analysis will be performed using either SAS version 9.3 or higher or R version 3.5 or higher.

Categorical data will be analyzed using Fisher's exact test using 0.05 level of significance ($\alpha = 0.05$) with Holm-Bonferroni adjustments whenever pairwise comparisons are made between more than two categories.

Continuous data will be compared between two treatment groups using a Two-sample T-test if the normality assumption is met or Wilcoxon Rank-Sum Test, otherwise. Response rates will be compared using a Fisher's Exact test. Significant differences will be detected based on a two-sided test with $p \leq 0.05$ ($\alpha = 0.05$). Comparisons will be accompanied by the point-estimate and 95% CI for each group.

Missing data: The analysis plan assumes that missing data are missing completely at random (MCAR) and analysis will be performed on the available data.

Individual subject data listings will be provided as separate appendices in the CSR. All summaries, statistical analyses, and individual subject data listings will be analyzed by using either SAS version 9.3 or higher or R version 3.5 or higher.

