7.2.3 Immune Response

The following are the endpoints of interest:

Primary Analysis Endpoints:

- IgG antibody responses to ID93 by ELISA at Days 0, 14, 56, 70, 84, and 224
 - Mean endpoint titer of ID93-specific antibodies for total IgG on for each treatment group.
 - The proportion of subjects with at least a 4-fold increase in ID93-specific IgG antibody levels on Days 14, 56, 70, 84, and 224 relative to baseline (Day 0).
 - Mean fold change from baseline (Day 0) in IgG antibody responses to ID93.
- T cell responses to ID93 by PBMC ICS on Days 0, 7, 14, 56, 63, 70, 84, and 224
 - The proportion of cells expressing any two of IFN- γ , TNF, IL-2, IL-4, IL-21, or CD154 in response to ID93.
 - The polyfunctionality based on expression of IFN- γ , TNF, IL-2, IL-4, IL-21, or CD154.
- T cell responses to ID93 by ELISpot on Days 0, 14, 56, 70, 84 and 224
 - The number of IFN- γ cytokine-secreting cells in PBMC samples in response to the ID93 antigen relative to baseline (Day 0) at Days 14, 56, 70, 84, and 224, as assayed by ELISpot.

Secondary and Exploratory Analysis Endpoints:

- IgG subclass antibody responses to ID93 by ELISA at Days 0, 14, 56, 70, 84, and 224

- The proportion of subjects with at least a 4-fold increase in ID93-specific IgG1, IgG2, IgG3, and IgG4 antibody levels on Days 14, 56, 70, 84, and 224 relative to baseline (Day 0).
- Mean endpoint titer of ID93-specific antibodies for IgG1, IgG2, IgG3, and IgG4 on for each treatment group.

Immune responses for each treatment group will be evaluated by calculating the response rate and magnitude of response to ID93 at all timepoints for each immunologic endpoint. Comparisons of response rates for IgG and cytokine responses between treatment groups will be made using Fisher's exact tests.

The magnitude of IgG and cytokine responses will be compared between treatment groups using a Two-sample T-test if normality assumption is met or Wilcoxon Rank-Sum Test, otherwise.

Percentages of CD4+ cells producing selected immune markers will be summarized by time point and compared between treatment groups.

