7.2.3.1 IgG Antibody Response to ID93

IgG antibody responses (Total IgG, IgG1, IgG2, IgG3, and IgG4) to the ID93 antigen will be measured by ELISA using serum collected from a given subject. Specimens from all time points for a given subject will be analyzed on a single ELISA plate. The plate will contain standards and controls that will be used to determine plate validity based on criteria established during assay validation.

At each timepoint, the IgG mean endpoint titer (**Total IgG MEPT**) value calculated from duplicates or triplicates will be reported.

At each post-injection timepoint, the following **Post:Pre Ratio** will be calculated:

$$\text{Post:Pre Ratio} = \frac{\text{MEPT (Post-Injection Timepoint)}}{\text{MEPT (Baseline Timepoint)}}$$

A subject will be considered an antibody positive **Responder** at a given timepoint if:

- a) System suitability criteria for a given ELISA are met; and
- b) The Post:Pre Ratio at that timepoint is ≥ 4 .

The following **listing** is planned:

- Humoral Response: IgG ELISA: IgG Antibody Response

- This listing will be organized by treatment group and will include: Subject ID, Visit Day, Collection Date, IgG MEPT, Post:Pre Ratio, Responder (Yes/No)

The following **tables** are planned:

- Humoral Response: IgG ELISA: IgG Antibody Response
 - This is a tabulation by Visit Day of the Total IgG MEPT, Post:Pre Ratio, and Responder status of each treatment group. The table will include descriptive statistics and a statistical comparison of each parameter between the two treatment groups.
- A Narrative Table will be prepared and will include
 - Percent responder status at each time point with p-value of the statistical comparison of the treatment groups

The following **figure** is planned:

- Humoral Response: IgG ELISA: IgG Antibody Response
 - IgG MEPT (log10) by study visit and treatment group.
 - Repeated for each IgG subclass
 - This will be a line plot with error bars representing +/- 95% CI.

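### The between-arm test for continuous immune endpoints hangs on an undefined normality check, with no stated scale, no adjustment for Day 0 as a covariate and no promised between-arm estimate

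*SAP*

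**What the plan says.** SAP 7.2.1 sets the general rule for continuous data: the two groups are compared "using a Two-sample T-test if the normality assumption is met or Wilcoxon Rank-Sum Test, otherwise". SAP 7.2.3 repeats it for the immune data: "The magnitude of IgG and cytokine responses will be compared between treatment groups using a Two-sample T-test if normality assumption is met", with Wilcoxon as the alternative. Protocol 11.5.3 has the same data-dependent logic, "using ANOVA when the distribution is Gaussian and Kruskal-Wallis when the distribution is non-Gaussian".

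Neither document names a normality test or threshold. Neither says whether normality is judged per arm or pooled, per visit or once per endpoint, or on what scale. The only scale named for IgG is in the figure specification in SAP 7.2.3.1: "IgG MEPT (log10) by study visit and treatment group".

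Day 0 is used in several places:
- One IgG endpoint is "Mean fold change from baseline (Day 0) in IgG antibody responses to ID93" (SAP 7.2.3).
- The ratio of post-injection to baseline mean endpoint titer (MEPT) is compared between groups at each visit (SAP 7.2.3.1).
- Change from baseline is tabulated for ICS and ELISpot (SAP 7.2.3.2.1 and 7.2.3.2.2).
- The IgG and ELISpot responder rules refer to Day 0 (SAP 7.2.3.1 and 7.2.3.3).

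No test includes Day 0 as a covariate. SAP 7.2.1 promises a point estimate and 95% CI within each group, but no estimate of the difference or ratio between groups.

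**The concern.** Protocol 2.2 calls this a bridging study, and the second immune goal in SAP 7.2.1 is to find out whether the two presentations differ. That needs one effect measure that means the same thing at every visit, with an interval. A t-test compares means and a Wilcoxon test compares ranks. If a check on the data picks between them, the p-values for one endpoint may not all concern the same quantity. If the scale is also open, the means could be arithmetic or geometric.

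Three further consequences follow:
- The ICS and ELISpot narrative tables show medians beside a p-value. If the t-test is selected, that p-value concerns means.
- Without a between-arm estimate and interval, a non-significant p-value cannot show how large a difference remains possible.
- Day 0 samples are scheduled for every subject. If Day 0 predicts response, leaving it out of the model gives away precision in a trial of 48.

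**Working it through.** **Inputs from the documents.** The level is 0.05 (SAP 7.2.1: "using 0.05 level of significance" for categorical data, and for continuous data "Significant differences will be detected based on a two-sided test with" p at or below 0.05). Group sizes are 25 and 23 (SAP Table 1). The protocol planned equal groups: "Subjects who meet all eligibility criteria will be randomized 1:1 into the two treatment groups". Immune analyses use the per-protocol population, so the numbers analysed may be smaller.

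**Assumed, because the documents give no values.** Lognormal titers; a true arm shift of 0.8 SD on the log scale; natural-log SD 0.3 to 1.5; correlation ρ between Day 0 and post-injection log titer of 0 to 0.7. The planned rule was read as Shapiro-Wilk at 0.05 in each arm on raw titers.

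**1. The plan's own figures.** No power, SD or effect size is stated for any immune comparison. The one computed design figure is Protocol Table 2, on safety: 1 − (1 − p)^n. For p = 0.05 and n = 20 this is 1 − 0.95^20 = 0.6415, against 64% stated. All twelve cells reproduce, but they do not bear on this point.

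**2. Normal approximation.** The information factor is √(25 × 23 / 48) = 3.461. The shift detectable with 80% power is (1.960 + 0.842) / 3.461 × √(1 − ρ²), which is 0.81 SD unadjusted and 0.77, 0.70 and 0.58 SD adjusted at ρ = 0.3, 0.5 and 0.7. Power at 0.8 SD is Φ(0.8 × 3.461 / √(1 − ρ²) − 1.960): 79% unadjusted, and 83%, 89% and 97% at the same ρ. At ρ = 0.6, Φ(3.461 − 1.960) is about 93%.

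**3. Simulated power, %** (3,000 runs per setting, Monte Carlo error up to about 0.9 points; range over the SDs):

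| ρ | Planned rule, raw titers | Fixed log t-test | Log ANCOVA on Day 0 | Post:Pre ratio (log t-test or Wilcoxon) |
|---|---|---|---|---|
| 0 | 74.9–76.6 | 76.9–77.6 | 75.5–77.3 | 45.4–48.5 |
| 0.3 | 74.8–75.7 | 76.2–77.9 | 78.5–81.0 | 58.7–64.5 |
| 0.5 | 74.0–76.9 | 76.1–78.5 | 86.4–87.6 | 74.1–78.3 |
| 0.7 | 75.7–77.0 | 77.0–78.4 | 96.3–97.2 | 92.0–95.5 |

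Compared within each SD, the fixed log t-test gains 0 to 3 points over the planned rule. ANCOVA gains about 0 to 2 points at ρ = 0, 3 to 6 at 0.3, 10 to 12 at 0.5 and 20 to 21 at 0.7. A separate run at ρ = 0.6 gave 92% for ANCOVA against 74–77% for the rule, a gain of at least 92 − 77 = 15 points. With 70% of Day 0 values at the floor, ANCOVA fell to 84–85%. Type I error was 4.8–5.9% for the planned rule and 4.9–5.6% for ANCOVA.

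**4. How often both tests appear within one endpoint.** This assumes a check at each of the five post-baseline visits, on raw titers, with a 0.8 SD shift (1,500 runs):

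| SD (log10) | Visit correlation 0.3 | Visit correlation 0.7 |
|---|---|---|
| 0.15 | 91% | 80% |
| 0.20 | 64% | 57% |
| 0.25 | 37% | 32% |
| 0.30 | 14% | 13% |
| 0.40 | about 1% | about 1% |
| 0.50 | 0% | 0% |

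With strong skew Wilcoxon is nearly always chosen, so switching disappears. If the data are truly normal on the scale checked, false alarms alone cause mixing. A visit passes with probability about 0.95² = 0.9025, and 1 − 0.9025^5 is about 40% for independent visits; simulation gave 37–41%.

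**5. One model serves titer and fold change.** If log10 post = a + b·arm + c·log10 Day 0, then log10 (post / Day 0) = a + b·arm + (c − 1)·log10 Day 0. The arm effect b is the same in both, and 10^b is the geometric mean ratio.

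**The case against.** The strongest case on the other side is that little is lost. Sample size was not based on power (SAP 7.1), and Protocol 11.3 says no formal hypothesis is tested. The rule holds its type I error and costs at most about 3 points of power. ICS and ELISpot values are floored at zero, so the rule would usually choose Wilcoxon there anyway. The planned Post:Pre ratio comparison is itself referenced to baseline and reaches 92–96% power at ρ = 0.7, close to ANCOVA. Subjects are QuantiFERON-negative with no earlier ID93 exposure, and titers below the limit of detection are set to that limit. Many Day 0 values may therefore sit at the floor and predict little.

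Most of this stands and limits the size of the point. It does not remove it. The ratio comparison is weakest where Day 0 predicts least: about 45–49% at ρ = 0, against 76–77% for ANCOVA. The plan also tests titer and ratio separately at each visit, so the two can disagree. The low cost of the rule is no reason to leave the test and scale open, and the missing between-arm estimate does not depend on any assumed correlation.

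The objection that ANCOVA carries its own distributional risk is partly right. A Day 0 covariate piled at the limit of detection breaks no model assumption, but post-injection titers piled there could, for example in weakly responding subclasses.

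A reader might infer that the plan ignores Day 0. It does not, as the fold change, change-from-baseline and responder rules show. A reader might also infer that normality will be tested at each visit on untransformed titers. By-visit tables make a by-visit check a natural reading, but the SAP is silent on both timing and scale.

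**Conclusion.** The point holds as one of under-specification with a modest, conditional cost. The SAP leaves the test to an undefined check, does not state the scale of analysis, does not adjust for Day 0 as a covariate, and promises no between-arm estimate with an interval. On a raw-scale check at each visit, the effect tested would often change between visits when skew is mild and rarely when it is strong.

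The documents do not support a claim that the choice rule itself loses material power or inflates type I error. The larger gains come from baseline adjustment and depend on a Day 0 correlation that the documents do not give. They shrink if most Day 0 titers lie at the limit of detection. At ρ = 0, adjusting costs about 0.3 to 1.4 points against an unadjusted log t-test, so the downside is small. All power figures rest on the assumed 0.8 SD shift, lognormal titers and 25/23 subjects. No power stated in the plan is contradicted.

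**What to change.** In SAP 7.2.1 and 7.2.3, delete the normality check for immune endpoints and fix the method in advance:

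- **Total IgG and subclasses:** ANCOVA of log10 MEPT at each post-baseline visit on arm and log10 Day 0 MEPT. Report the single-vial to two-vial geometric mean ratio with 95% CI. State that this is also the arm effect on log fold change. Report how many values sit at the limit of detection at each visit, and name a Wilcoxon test as sensitivity analysis where many post-injection values do.
- **ICS and ELISpot:** Wilcoxon rank-sum at every visit, zeros included, with a Hodges-Lehmann shift and 95% CI beside the medians.

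The cost is SAP wording and standard code in SAS or R. No new samples or visits are needed, and the present SAP amendment already concerns only the immunology section. The change should be dated before the immune data are compared by arm; if that has already happened, the new analyses should be labelled as specified afterwards.

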7.2.3.2.1 ICS

PBMC ICS will be performed on Days 0, 7, 14, 56, 63, 70, 84, and 224 to determine the proportion of single and multi-functional CD4 and CD8 T-cells producing various combinations of IFN- γ , TNF, IL-2, IL-4, IL-21, and CD154 in response to ID93 stimulation. A gate is applied for each functional marker, not accounting for co-expression of other markers. Boolean gates are later created based on the gates shown to identify cells expressing various combinations of markers. We will analyze the T cell population “Any Two”, which are positive for at least two immune markers among IFN- γ , TNF, IL-2, IL-4, IL-21, and CD154. We will also evaluate T cells that express selected combinations of the six immune markers. The selected combinations will be indicated in the data set. Any negative background-subtracted values will be set to zero.

The following **listing** is planned to be presented:

- Cellular Response: PBMC ICS: T cell Response
 - Percent immune marker-positive (“Any Two” and for selected combinations of the six), background-subtracted cytokine response, change from baseline, fold change from baseline, and responder status

Tabular summaries will present “Any Two” immune marker-positive and polyfunctional responses (only background-subtracted non-zero values will be presented). T-cell response frequencies will be summarized by treatment regimen. Percentages will be based on the total number of subjects within each treatment group. The following **tables** are planned for presentation:

- Cellular Response: PBMC ICS: T cell Response and Change from Baseline
 - Percent immune marker-positive background-subtracted T cell response (“Any Two” and for selected combinations of the six) and change from Baseline, including N, Median, and 95% CI for each parameter.
- A Narrative Table will be prepared and will include
 - Medians of the “Any Two” CD4 and CD8 T cell responses per treatment group and study visit with p-value of the statistical comparison of the treatment groups

- Responder Rate of the “Any Two” CD4 and CD8 T cell responses per treatment group and study visit with p-value of the statistical comparison of the treatment groups

The following **figures** are planned:

- Cellular Response: PBMC ICS: T Cell Response Magnitude by Study Day
 - Background-subtracted total T cell subject response (“Any two”) by visit and by T cell type.

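### The immunogenicity comparison is planned as p-values plus a separate interval for each group; no estimate or interval for the difference between the two presentations is specified

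*SAP*

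**What the plan says.** Protocol 3.1 and SAP 2.2 make the comparison of the two presentations' immunogenicity a secondary objective. Protocol 2.2 calls the trial a bridging study. Protocol 11.3 says that no formal hypothesis is being tested, and SAP 7.1 that the sample size does not rest on power.

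SAP 7.2.1 gives the second goal of the immune-response analysis as "To determine if there is a significant difference in the immune response elicited by the two-vial and the single-vial lyophilized vaccine presentation". The tools are a t-test or Wilcoxon rank-sum test for magnitudes and Fisher's exact test for response rates, two-sided at 0.05. The estimation clause is "Comparisons will be accompanied by the point-estimate and 95% CI for each group".

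The assay sections follow this pattern:

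- **IgG (SAP 7.2.3.1).** Main table: "The table will include descriptive statistics and a statistical comparison of each parameter between the two treatment groups". Narrative table: "Percent responder status at each time point with p-value of the statistical comparison of the treatment groups". A figure shows log10 mean endpoint titre by visit and group with 95% CI bars.
- **ICS (SAP 7.2.3.2.1).** The main table gives N, median and 95% CI. The narrative table gives medians and responder rates for the Any Two "CD4 and CD8 T cell responses per treatment group and study visit with p-value of the statistical comparison of the treatment groups". On zeros: "Any negative background-subtracted values will be set to zero", and in the tables "only background-subtracted non-zero values will be presented".
- **ELISpot (SAP 7.2.3.2.2).** Descriptive statistics with a 95% CI for the median, then medians and responder rates with a p-value.

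Protocol 11.5.3 lists tests only. SAP 7.2.1 also says: "All individual subject data listings will be provided in appendices to the clinical study report".

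**The concern.** In a bridging comparison that was not sized for power, the useful result is how large a difference the data still allow. A p-value does not show that, and two separate group intervals show it only indirectly. At about 24 subjects per group, a non-significant p-value can coexist with a difference that would matter to someone deciding whether the new presentation can stand in for the old one. As goal 2 is worded, the result to report is whether significance was reached.

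The between-group quantity is not hidden elsewhere in the plan. The Post:Pre ratio, fold change and change from baseline are within-subject measures. The odds ratios in SAP 7.2.3.3 compare antigen with DMSO within one subject to set ELISpot responder status. The statistical comparison promised for the main IgG table has no defined content, so an interval there is neither required nor excluded.

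**Working it through.** **The plan's own figure.** The only design calculation is Protocol Table 2, which concerns safety. It follows 1 − (1 − p)^n, and all 12 cells reproduce within rounding (for example p = 0.10, n = 20: 87.8% against the printed 88%). No figure is given for immunogenicity, so what follows is illustration.

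**Inputs.** From the documents: 25 two-vial and 23 single-vial subjects (SAP Table 1), and two-sided alpha 0.05 (SAP 7.2.1). Assumed: log10-titre SD 0.5, range 0.3 to 0.8; a t-test on log10 titre (the SAP states no transformation for testing); a true halving of titre.

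**Width of the missing interval.** Half-width = t(0.975, 46) × SD × √(1/25 + 1/23) = 2.013 × 0.2889 × SD = 0.582 SD. Back-transformed, the factor for the ratio of geometric mean titres is 10^(0.582 SD):

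| SD (log10) | Factor, 25/23 | Halving non-significant at one visit |
|---|---|---|
| 0.3 | 1.49 | 7.5% |
| 0.5 | 1.95 | 47% |
| 0.8 | 2.92 | 75% |

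The last column is from the noncentral t with noncentrality log10(0.5)/(SD × 0.2889); at SD 0.5 that is −0.301/0.1445 = −2.08. With an assumed per-protocol loss to 22/20, the factor at SD 0.5 is 2.05.

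**Group intervals read by eye.** Two separate 95% CIs stop overlapping at t(0.975, 24)/√25 + t(0.975, 22)/√23 = 0.85 SD. The test reaches p = 0.05 at 0.58 SD. Judging by overlap therefore misleads between those values.

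**What a reader could rebuild.** For IgG at SD 0.5, the group half-widths are 2.064 × 0.5/√25 = 0.206 and 2.074 × 0.5/√23 = 0.216. Their root sum of squares is 0.299, a factor of 1.99 against the direct 1.95, so the planned log10 figure gives a good approximation. For responder rates, the Newcombe interval needs only the counts. With hypothetical counts of 18/23 and 20/25, Fisher p = 1.0 and the difference is 0.783 − 0.800 = −0.017. The Wilson limits are 0.581 to 0.903 and 0.609 to 0.911. Hence:

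- lower limit: −0.017 − √(0.202² + 0.111²) = −0.25
- upper limit: −0.017 + √(0.121² + 0.191²) = +0.21

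A p-value of 1.0 thus sits beside an interval from −25 to +21 points.

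**What is harder.** Group medians with their own CIs do not combine into an interval for a shift. For ICS, negative values become zero and zeros are left out of the tables, so a difference in the share of zeros would not appear there.

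**Limit of the remedy.** A Hodges-Lehmann interval can collapse to exactly 0 to 0 when zeros are many. In simulation (25/23, 6,000 trials per setting, non-zero values assumed lognormal(0,1), equal zero fractions) this happened in 0% of trials at 30% zeros, 0.1% at 40%, 3% at 50%, 24% at 60% and 66% at 70%. With 80% against 60% zeros it happened in 39%.

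**The case against.** The strongest reply is that little is lost. This is a phase 1 study offering preliminary information, and goal 1 in SAP 7.2.1 is already descriptive. Each group gets an estimate and an interval, the IgG figure lets a reader rebuild the ratio interval almost exactly, responder counts suffice for a risk difference, and subject listings allow anything else to be derived. ICS zeros remain visible in the planned dot plots. All the sizes above depend on an assumed SD and an assumed halving.

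Most of this stands, and it limits the point to reporting and interpretation. It does not remove the gap. No difference is planned for any endpoint, the ICS and ELISpot medians cannot readily be converted, and an interval chosen after the data are seen carries less weight than one specified beforehand.

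A reader might go further and infer that the SAP treats p > 0.05 as showing the presentations to be alike, or that the planned tests are wrong. The documents support neither. No passage claims comparability or sets a margin, and the tests are standard for the question asked. Nor is the difference unrecoverable, given the listings, the counts and the IgG figure.

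**Conclusion.** The omission is confirmed across SAP 7.2.1 and 7.2.3 with its subsections, and Protocol 11.5.3. It is worth correcting, but it is not an error in the tests or in any stated number. Under the assumptions above, an IgG comparison at one visit is uncertain by a factor of about 2 either way (1.5 to 2.9), and a halving would be missed about as often as found at SD 0.5. The 7.5% to 75% spread shows how strongly this depends on an SD that the documents do not give. The need is greatest for the ICS and ELISpot magnitudes and least for total IgG and responder rates.

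**What to change.** Change the immunology section only and keep every planned test. Beside the p-values for total IgG, ICS Any Two and ELISpot to ID93 (Tables 14.3.1 to 14.3.5 and narrative Tables 10 to 13), report:

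1. **Total IgG:** the single-vial to two-vial ratio of geometric mean titres, and of geometric mean fold rises, each with a 95% CI. State that log-scale means are used, because the SAP says only mean.
2. **Responder rates:** the risk difference with Newcombe 95% CI for IgG and ELISpot. Do the same for ICS once its responder rule is written; SAP 7.2.3.3 gives rules only for ELISA and ELISpot.
3. **ICS and ELISpot magnitude:** the number and proportion of zeros per group, and a Hodges-Lehmann shift with 95% CI, flagged as uninformative where zeros are many.

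Reword goal 2 as estimating the difference between presentations, and state that p > 0.05 is not evidence of comparability.

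**Cost.** No new data. About 63 intervals: total IgG 5 post-baseline visits × 3 = 15; ICS 7 visits × 2 cell types × 2 = 28; ELISpot 5 visits × 2 analytes × 2 = 20. IgG subclasses, selected ICS combinations or further stimulation antigens would add more. Wide intervals will be on show, and a log-scale CI may disagree with a Wilcoxon or raw-scale p-value, which needs a footnote.
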